8.3.9. Nausea Improvement

The Nausea Improvement assessment is a 5-category response scale asking whether the participant experienced any improvement in nausea symptoms over the course of the study and, if so, the level of importance.

This assessment will be conducted as an End of Study assessment.

8.4. Safety Assessments

Planned time points for all safety assessments are provided in the SoA ([Section 1.3](#)).

8.4.1. Physical Examinations

A complete physical exam, including neurologic, cardiovascular, pulmonary, abdominal and breast exams, will be performed at Screening, Day 1, and Weeks 4, 8, and 12 as well as at the Follow-up Visit. Weight will be measured at all visits. Height (without shoes) will also be measured and recorded on Day 1. Investigators should pay special attention to clinical signs related to previous serious illnesses. For female participants, menstrual cycle will be recorded during the study.

Only clinically significant changes in physical examination findings will be recorded at subsequent visits, as indicated in the SoA ([Section 1.3](#)).

8.4.2. Vital Signs

Vital signs, including oral temperature, pulse rate, respiratory rate, and BP will be measured at each study visit while the participant is in the sitting position. A standardized oscillometric automated BP device will be used; manual auscultatory assessment will be used only if the BP reading cannot be captured by the standardized automated device (eg, based on specific physiologic condition, or if the automated device is not functional). Blood pressure and pulse measurements should be preceded by at least 5 minutes of rest for the participant in a quiet setting without distractions (eg, television, cell phones). Additional information regarding the standardized automated office BP assessment will be outlined in the training manual provided by the cardiac safety laboratory.

Orthostatic vital signs will be assessed as follows (and as clinically indicated; see also the SoA in [Section 1.3](#)).

- At Screening, BP and heart rate will be measured while sitting and after 1 minute in the standing position.
- At the Day 1 Visit, BP and heart rate will be measured before dosing and at 1, 2, and 3 hours after dosing. Measurements will be done while the participant is sitting, as well as after 1 minute in the standing position.
- At the Week 1 Visit, BP and heart rate should be measured before dosing and at 1 hour after dosing. Measurements will be done while the participant is sitting, as well as after 1 minute in the standing position.
- At the Week 2 visit, BP and heart rate will be measured before dosing, and at 1, 2, and 3 hours after dosing. Measurements will be done while the participant is sitting, as well as after 1 minute in the standing position.

For participants in the Intensive PK subset, in addition to the assessments described above, orthostatic vital signs will also be assessed at the Day 1 and Week 2 visits at hours 4, 5, and 6, as well as 1 and 2 hours after the second dose in the clinic on Day 1.

8.4.3. *Electrocardiograms*

TriPLICATE 12-lead ECGs will be obtained as outlined in the SoA (see [Section 1.3](#)) using an ECG machine that automatically calculates the heart rate and measures PR, QRS, QT, and QTcF intervals.

At each time point at which triplicate ECG are required, 3 individual ECG tracings should be obtained as closely as possible in succession, but no more than 2 minutes apart. The full set of triplicates should be completed in less than 4 minutes.

Participants must rest in the recumbent position for at least 10 minutes before the ECG recording is started. A qualified physician will review the ECGs promptly and any clinically important finding will be recorded on the appropriate CRF. The investigator is responsible for reviewing all ECGs. All ECGs will also be centrally read.

8.4.4. *Clinical Safety Laboratory Assessments*

See [Appendix 10.3](#) for the list of clinical laboratory tests to be performed and the SoA for the timing and frequency.

All clinical laboratory assessments will be conducted by a central laboratory. The use of local laboratories is allowed in cases where safety assessment is time sensitive and the central laboratory results will not be available before potential actions need to be taken for safety reasons.

The investigator must review the laboratory report, document this review, and record any clinically relevant changes occurring during the study in the AE section of the CRF. The laboratory reports must be filed with the source documents. Clinically significant abnormal laboratory findings are those which are not associated with the underlying disease, unless judged by the investigator to be more severe than expected for the participants condition.

All laboratory tests with values considered clinically significantly abnormal during participation in the study should be repeated until the values return to normal or baseline or are no longer considered clinically significant by the investigator or medical monitor

- If such values do not return to normal/baseline within a period of time judged reasonable by the investigator, the etiology should be identified, and the sponsor notified.
- All protocol-required laboratory assessments, as defined in [Appendix 10.3](#), must be conducted in accordance with the laboratory manual and the SoA.
- If laboratory values from non-protocol specified laboratory assessments performed at the institution's local laboratory require a change in participant management or are considered clinically significant by the investigator (eg, SAE or AE or dose modification), then the results must be recorded in the CRF.

8.5. Adverse Events and Serious Adverse Events

AEs will be reported by the participant (or, when appropriate, by a caregiver, surrogate, or the participant's legally authorized representative).

The investigator and any qualified designees are responsible for detecting, documenting, and recording events that meet the definition of an AE or SAE and remain responsible for following up AEs that are serious, considered related to the study drug or study procedures, or that caused the participant to discontinue the study drug (see [Section 7](#)).

8.5.1. Time Period and Frequency for Collecting AE and SAE Information

All AEs and SAEs will be collected starting after the ICF is signed until the End of Study / Follow-up Visit as specified in the SoA ([Section 1.3](#)).

All SAEs will be recorded and reported to the sponsor or designee immediately and under no circumstance should this exceed 24 hours, as indicated in [Appendix 10.5.4](#). The investigator will submit any updated SAE data to the sponsor within 24 hours of it being available.

Investigators are not obligated to actively seek AE or SAE after conclusion of the study participation. However, if the investigator learns of any SAE, including a death, at any time after a participant has been discharged from the study, and he/she considers the event to be reasonably related to the study drug or study participation, the investigator must promptly notify the sponsor.

8.5.2. Method of Detecting AEs and SAEs

The method of recording, evaluating, and assessing causality of AE and SAE and the procedures for completing and transmitting SAE reports are provided in [Appendix 10.5](#).

Care will be taken not to introduce bias when detecting AEs and/or SAEs. Open-ended and non-leading verbal questioning of the participant is the preferred method to inquire about AE occurrences.

8.5.3. Follow-up of AEs and SAEs

After the initial AE/SAE report, the investigator is required to proactively follow each participant at subsequent visits / contacts. All AEs considered related to study drug, SAEs, (and AEs of special interest, as defined in [Section 8.5.7](#)), will be followed until resolution, stabilization, the event is otherwise explained, or the participant is lost to follow-up (as defined in [Section 7.3](#)). Further information on follow-up procedures is provided in [Appendix 10.5.3](#).

8.5.4. Regulatory Reporting Requirements for SAEs

Prompt notification by the investigator to the sponsor of a SAE is essential so that legal obligations and ethical responsibilities towards the safety of participants and the safety of a study drug under clinical investigation are met.

The sponsor has a legal responsibility to notify both the local regulatory authority and other regulatory agencies about the safety of a study drug under clinical investigation. The sponsor will comply with country-specific regulatory requirements relating to safety reporting to the

regulatory authority, Institutional Review Boards (IRB)/Independent Ethics Committees (IEC), and investigators.

For all studies except those utilizing medical devices investigator safety reports must be prepared for suspected unexpected serious adverse reactions (SUSAR) according to local regulatory requirements and sponsor policy and forwarded by the sponsor (or designee) to investigators as necessary.

An investigator who receives an investigator safety report describing a SAE or other specific safety information (eg, summary or listing of SAEs) from the sponsor will review and then file it along with the IB and will notify the IRB/IEC, if appropriate according to local requirements.

8.5.5. Pregnancy

Details of all pregnancies in female participants and female partners of male participants will be collected after the start of study drug and the participant will be followed until the outcome of the pregnancy is known.

If a pregnancy is reported, the investigator should inform the sponsor within 24 hours of learning of the pregnancy and should follow the procedures outlined in [Appendix 10.6](#).

Abnormal pregnancy outcomes (eg, spontaneous abortion, fetal death, stillbirth, congenital anomalies, ectopic pregnancy) are considered SAEs.

8.5.6. Disease-Related Events and/or Disease-Related Outcomes Not Qualifying as AEs or SAEs

Worsening of gastroparesis will not be considered an AE since it is captured by PRO efficacy assessments. However, the signs, symptoms, and / or clinical sequelae resulting from worsening of disease will be reported as an SAE if the definition of an SAE is fulfilled, or if they are considered by the investigator not to be adequately captured by the protocol-specified disease-related assessments (see [Appendix 10.5.1](#) and [Appendix 10.5.2](#), respectively).

8.5.7. Adverse Events of Special Interest

Treatment-emergent AESIs are based on the known effects of D₂ and alpha-1 antagonists, as well as observations in the nonclinical and phase 1 studies. The rationale for inclusion of each TEAESI is provided in [Table 3](#) below:

Table 3: Adverse Events of Special Interest: Rationale for Inclusion and Criteria for Diagnosis

AESI	Rationale and Criteria for Diagnosis
Gynecomastia	Rationale: Effects of treatment with NG101 in animals were consistent with the non-CNS effects seen with other D ₂ antagonists. These are considered secondary to increased prolactin levels resulting from D ₂ receptor antagonism.
Galactorrhea	
Menstrual irregularity	Criteria for diagnosis: Per the opinion of the treating investigator.
Decreased libido	
Impotence	
Extrapyramidal symptoms (EPS)	Rationale: Although metopimazine is not expected to penetrate the CNS, AEs from central D ₂ blockade may include events of EPS. Criteria for diagnosis: Extrapyramidal symptoms can include events categorized as acute (dystonia, akathisia and parkinsonism) or tardive (tardive dyskinesia and tardive dystonia; Pierre 2005).
Neuroleptic malignant syndrome (NMS)	Rationale: Although metopimazine is not expected to penetrate the CNS, AEs from central D ₂ blockade may include events of NMS. Criteria for diagnosis: Neuroleptic malignant syndrome is considered in cases with recent dopamine antagonist exposure, or dopamine agonist withdrawal. Clinical features include hyperthermia; rigidity; mental status alteration; creatine kinase elevation; sympathetic nervous system lability; tachycardia plus tachypnea; and a negative work-up for other causes. The following are critical values for quantitative criteria (Gurrera et al. 2011): hyperthermia, > 100.4°F or > 38.0°C on at least 2 occasions; creatine kinase elevation, at least 4 x ULN; blood pressure elevation \geq 25% above baseline; blood pressure fluctuation, \geq 20 mm Hg (diastolic) or \geq 25 mm Hg (systolic) change within 24 hours; tachycardia, \geq 25% above baseline; and tachypnea, \geq 50% above baseline.

Orthostatic hypotension (OH)	
Rationale: OH was observed in phase 1 studies, and likely occurs due to partial inhibition of α-1 receptors.
 
Criteria for diagnosis: OH is defined by a decrease in systolic BP of at least 20 mm Hg, and/or decrease in diastolic BP of at least 10 mm Hg, with associated severe postural symptoms.
 
Postural AEs can include feelings of lightheadedness, general weakness, warmth, diaphoresis, nausea, palpitations or blurry vision
 
(Whitledge et al. 2019). Severe postural symptoms include presyncope, syncope, and other severe AEs that are considered of substantial clinical relevance by the investigator. Presyncope is defined as “feeling like one was going to pass out but without actual loss of consciousness”
 
(Whitledge et al. 2019). Syncope is “the sudden loss of consciousness, associated with inability to maintain postural tone, with immediate and spontaneous recovery without requiring electrical or chemical cardioversion”
 
(da Silva 2014).

-------------------------------------	---

Abbreviations: AE = adverse event; AESI = adverse event of special interest; BP = blood pressure; CNS = central nervous system; D₂ = dopamine receptor; EPS = extrapyramidal symptoms; NMS = neuroleptic malignant syndrome; OH = orthostatic hypotension; ULN = upper limit of normal.

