1.3. Schedule of Activities (SoA)

Procedure	Screening Visit	Pre-treatment Visit	Treatment Period Visits						E/D Visit	EoS / Follow-up Visit	Notes	
	(up to 28 days before Day -14)	Day	Day	Week								
		-17 to -14	1	(± 2d)	2	(± 2d)	4	(± 2d)	8	(± 3d)	12	(± 3d)
Informed consent	X											
Inclusion and exclusion criteria	X		X									Recheck clinical status / check compliance before randomization on Day 1
Demography	X											
Medical history	X											Including prior treatments for gastroparesis (dose, regimen, duration), substance use and, for females, menstrual history
Gastric emptying test	X											FDA-approved breath test completed and assessed for eligibility in participants who have not completed the breath test or scintigraphy test within 12 months prior to Screening, or during the Screening Period. Must be a minimum of 7 days between the gastric emptying study and the start of the Pretreatment Period.

Procedure	Screening Visit	Pre-treatment Visit	Treatment Period Visits						E/D Visit	EoS / Follow-up Visit (14 ± 3 days after last dose)	Notes	
	(up to 28 days before Day -14)	Day	Day	Week								
		-17 to -14	1	(± 2d)	2	(± 2d)	4	(± 2d)	8	(± 3d)	12	(± 3d)
Physical examination	X		X				X	X	X	X	X	A physical exam including neurologic, cardiovascular, pulmonary, abdominal and breast exams will be performed at Screening, Day 1, and Weeks 4, 8, and 12 (or E/D) as well as at the Follow-up Visit. Height will be measured on Day 1. For females, menstrual cycle will be recorded during the study.
Weight	X	X	X	X	X	X	X	X	X	X	X	
Vital signs	X	X	X	X	X	X	X	X	X	X	X	Vital signs include oral temperature, pulse rate, respiratory rate, and blood pressure. Orthostatic vital signs will also be checked at Screening, and at the Day 1, Week 1, and Week 2 visits. See Section 8.4.2 .

Procedure	Screening Visit	Pre-treatment Visit	Treatment Period Visits						E/D Visit	EoS / Follow-up Visit (14 ± 3 days after last dose)	Notes	
	(up to 28 days before Day -14)	Day	Day	Week								
		-17 to -14	1	(± 2d)	2	(± 2d)	4	(± 2d)	8	(± 3d)	12	(± 3d)
12-lead ECG	X		X		X			X	X	X		On Day 1 and Week 2, ECGs will be performed in triplicate at the time of PK sampling (ie, predose and at 1 [near anticipated T_{max}], 2, and 3 hours postdose). For the Intensive PK subset, in addition to the ECG assessments described above, triplicate ECGs should be taken at hour 6 (on Day 1 and Week 2) as well as 1 and 2 hours after the second dose at the Day 1 visit. See Section 8.4.3 .

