Metopimazine was rapidly metabolized to metopimazine acid, with metopimazine acid C_{max} occurring at median times ranging from 2 to 3 hours after dosing across cohorts. The mean metopimazine acid elimination $t_{1/2}$ ranged from 2.7 to 3.5 hours. Relative to parent metopimazine, plasma metopimazine acid exposure was generally 3- to 4-fold higher for C_{max} and 6- to 11-fold higher for AUC. For metopimazine, a close to dose proportional increase was observed for C_{max} , AUC from time 0 to the last measurable concentration (AUC_{0-last}) and AUC_{0-inf} . Accumulation of metopimazine acid was observed after repeated doses (Q6H) with a mean accumulation ratio of 1.6 to 1.7 based on C_{max} and 1.7 to 1.9 based on AUC_{0-6} .

Safety

No serious adverse events (SAEs) were observed during the study, and no participants withdrew due to adverse events (AEs). All adverse events (AEs) were reported to be mild or moderate in severity. No symptoms suggestive of neuroleptic malignant syndrome (NMS) or extrapyramidal symptoms (EPS) were observed and there were no clinically relevant changes in electrocardiogram (ECG) time intervals. No notable trends were observed in changes in laboratory tests.

An increased risk of orthostatic hypotension (OH) was observed with metopimazine, likely due to inhibition of peripheral adrenergic alpha-1 receptors. Orthostatic changes in vital signs considered to be clinically significant were defined as a decrease in systolic or diastolic blood pressure (BP) of at least 20 mm Hg or 10 mm Hg, respectively, or heart rate increase of at least 30 beats/minute and/or heart rate above 120 beats/minute ([Freeman et al. 2011; NIH-NINDS Postural Tachycardia Syndrome Information Page 2019](#)).

In the 15 mg and 30 mg groups of the SAD portion of the study, 1 to 2 participants (out of 6 in each dose group) were reported to have “dizziness in standing position”. No vital sign measurements were obtained at the time of these events; however, the preferred term of OH was recorded. A protocol amendment was implemented after cohort 2 (30 mg) of the SAD portion of the study to require vital sign measurements lying, sitting, and standing at prescribed timepoints after dosing. In the 45 mg and 60 mg groups of the SAD, 4 participants (out of 6 in each dose group) experienced OH.

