Following oral administration of 15 mg of metopimazine as NG101 in fasted conditions, metopimazine plasma peaks occurred at a median time of 0.75 hours after dosing. Mean metopimazine C_{max} and AUC_{0-2h} values were 20.6 ng/mL and 39.9 ng.h/mL, respectively. A lag time of 0.25 hours (median) was observed after dosing. The terminal elimination rate constant (Lambda z) and the derived parameters ($t_{1/2}$, AUC_{inf} , Cl/F and Vd/F) could not be reliably determined. A high inter-individual variability was observed with %CV between 60.4 and 82.6%. Metopimazine C_{max} and AUC_{0-2h} appeared to be approximately dose proportional between the 7.5 mg dose of NG101 in Cohort 1 and the 15 mg dose in Cohort 2.

Safety

No serious adverse events (SAEs) were observed during the study, and no participants withdrew due to adverse events (AEs). All adverse events (AEs) were reported to be mild or moderate in severity. In each of the three 15-participant treatment groups, 2 to 4 participants reported AEs that were related to postural change (consistent with results observed in the SAD / MAD study). However, no consistent pattern was observed within individual participants across the treatments (ie, some participants had the AEs with 1 treatment but not another). A small increased risk of orthostatic related AEs was observed upon fasting (ie, 3 fasting versus 1 fed). All OH events occurred at 1 hour after dosing, with the exception of 1 OH event that occurred at hour 8. There were no other trends indicative of clinically important treatment-related laboratory abnormalities.

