7.1. Discontinuation of Study Drug

In rare instances, it may be necessary for a participant to permanently discontinue (definitive discontinuation) study drug. If study drug is definitively discontinued, the participant will remain in the study to be evaluated for follow-up.

If a clinically significant finding in clinical laboratory or ECG parameters is identified (including, but not limited to changes from baseline in QT interval corrected using Fridericia's formula [QTcF] after enrollment), the investigator or qualified designee will determine if the participant can continue in the study and if any changes in participant management are needed. This review of the ECG printed at the time of collection must be documented. Any new clinically relevant finding should be reported as an AE.

For any female participants, or partners of male participants, who become pregnant during the study, see guidance in [Appendix 10.6](#).

See the SoA for data to be collected at the time of discontinuation of study drug and follow-up, and for any further evaluations that need to be completed ([Section 1.3](#)).

Criteria for Withdrawal from Treatment:

- AE(s) which, in the opinion of the investigator or sponsor, make continued treatment in the study inappropriate
- AEs consistent with EPS, such as acute dyskinesias and dystonic reactions, tardive dyskinesia, Parkinsonism, akinesia, or akathisia.
- Neuroleptic malignant syndrome.
- Worsening of gastroparesis signs and/or symptoms that cannot be adequately controlled by the participant's current treatment regimen (including the protocol-allowed rescue treatment), and thus make continued treatment in the study inappropriate.
- Significant non-compliance
- Withdrawal of consent to receive the study treatment
- Orthostatic hypotension (decrease in systolic BP of at least 20 mm Hg) with associated severe postural symptoms (including presyncope, syncope, and other severe AEs that are considered of substantial clinical relevance by the investigator). See [Table 3](#) for additional details and definitions.
 - Participants meeting this discontinuation criterion while under observation during clinical visits must be monitored in the clinic until postural symptoms are no longer severe, and will be withdrawn from the study. Participants who develop severe postural symptoms at home will hold any further dosing and return to the study site as soon as possible for further evaluation.

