8.6. Treatment of Overdose

For this study, participants are expected to take no more than 4 capsules in 1 day.

In the event of an overdose, participants should notify the investigator and the investigator should:

1. Contact the Medical Monitor immediately.
2. Continue to monitor the participant for any AE / SAE and laboratory abnormalities
3. Document the quantity of the excess dose.
4. Consider skipping the next dose of NG101. NG101 can be reinitiated, with the timing depending on the amount of overdose and considering the half-life of metopimazine (approximately 2 hours). Reinitiation should be discussed with the medical monitor.

Participants should be treated according to the symptoms they are experiencing. If a participant has symptoms suggestive of orthostasis, then the participant should sit down or lie down, depending on the severity of symptoms. Participants will be trained to recognize the signs and symptoms of OH.

Decisions regarding dose interruptions or modifications will be made by the investigator in consultation with the Medical Monitor based on the clinical evaluation of the participant.

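### Table 3 counts orthostatic hypotension as an AESI only when a blood-pressure fall accompanies severe symptoms, so a home syncope or presyncope with no captured fall is left out of the by-arm OH row

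*Combined protocol and SAP*

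**What the plan says.** - **Definition.** The OH entry in Table 3 (Section 8.5.7) begins "OH is defined by a decrease in systolic BP of at least 20 mm Hg". It adds a diastolic fall of at least 10 mm Hg, joined by and/or, and asks for associated severe postural symptoms. Presyncope and syncope are named as examples of such symptoms. Neither is an AESI in its own right.
- **Contrast within the table.** For the prolactin-related AESIs the rule is "Criteria for diagnosis: Per the opinion of the treating investigator". The OH entry has no such route.
- **Scheduled readings.** The Schedule of Activities (Section 1.3) states: "Orthostatic vital signs will also be checked at Screening, and at the Day 1, Week 1, and Week 2 visits". Section 8.4.2 gives predose and 1, 2 and 3 hour readings on Day 1 and at Week 2. For Week 1 it says: "At the Week 1 Visit, BP and heart rate should be measured before dosing and at 1 hour after dosing". Other readings are taken only when clinically indicated.
- **Events at home.** Section 7.1 says: "Participants who develop severe postural symptoms at home will hold any further dosing and return to the study site as soon as possible". It plans no home blood-pressure measurement and does not say how to classify the event if standing pressure is normal on return.
- **Reporting.** Section 9.3.6 summarizes AESIs by treatment group. It mentions alpha-1 antagonist effects as an example but lists no terms. It also summarizes all treatment-emergent events by arm, maximum severity and relationship to drug.

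**The concern.** OH is the clearest dose-dependent harm in the phase 1 data (Sections 2.2.1.1 and 4.3). AESI incidence is part of the primary safety endpoint (Section 3), and the trial is meant to guide the phase 3 dose (Section 2.3). A reader comparing arms will look first at the OH AESI row.

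That row rests on a definition with two required parts, one of which is a reading. Most doses are taken at home, where no reading is planned. A participant who faints at home has the symptom part in full but may never have the blood-pressure part documented. The row could then omit some of the most serious postural events, or include them only where a site happened to record OH rather than syncope as the diagnosis.

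**Working it through.** The plan states no figure on this point, so the check sets the provisions side by side and follows one event through them.

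**1. Is a fall strictly required?** Yes. The symptom clause comes after both blood-pressure limits and is most naturally read as applying to both. The stopping criterion in Section 7.1 likewise pairs a systolic fall with severe symptoms. Even if the symptom clause were attached to the diastolic limit alone, each route into the definition would still need a fall.

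**2. How much dosing has a scheduled reading?** Four doses a day for 12 weeks is 4 × 7 × 12 = 336 doses. Scheduled on-treatment orthostatic readings surround three dosing occasions (Day 1, Week 1, Week 2), or four in the intensive PK subset, which also has readings after the second Day 1 dose. This is a count of doses, not of risk, because phase 1 OH clustered at the start of dosing (step 5).

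**3. Where does a home event go?** Take a syncope at home, dosing held, and a normal standing pressure on return.

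| Place in the plan | Is the event counted? |
|---|---|
| OH AESI, Table 3 criteria | No: no fall documented |
| Any other AESI in Table 3 | No: syncope and presyncope are not listed separately |
| Treatment-emergent events by arm, severity and relationship (Section 9.3.6) | Yes |
| Serious events by arm (Section 9.3.6) | Yes, if a seriousness criterion is met |
| Safety board trigger (Section 9.5) | Can count, if it leads to discontinuation: the wording is OH-related events and is not tied to Table 3 |
| Withdrawal from treatment (Section 7.1) | Open to the investigator under the general adverse event criterion, even if the OH criterion is not met |

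**4. What if the row follows the recorded term instead?** Section 10.5.3 asks the investigator to reach a diagnosis from signs, symptoms or other clinical information, so OH could be recorded without a reading. The event then enters the row only if the investigator wrote OH rather than syncope or presyncope. The text does not say which basis the row uses.

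**5. What bears on size?**
- Repeat dosing at 15 and 30 mg every 6 hours: two participants and one participant had OH, all on Day 1 at Hour 1, with none on later dosing (Section 2.2.1.1, repeated in Section 4.3). The top dose here, 20 mg, lies between these two.
- The 20 mg arm takes 5 mg for 4 days and 10 mg for 3 days first. Section 2.5.1 expects repeated dosing to lessen the pressure effect.
- Day 1 readings cover the early window in every arm, and Week 2 readings cover the 20 mg arm at its full dose.
- One thin spot remains. The first 20 mg dose falls on Day 8 (Section 1.2), the Week 1 visit has a 2-day window, and its clinic dose need not be the first of the day (Section 6.1). A reading after that particular dose is therefore not guaranteed.

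The expected number of missed events in an arm would be participants × rate of severe home postural events × probability that no fall is captured. The documents give neither the rate nor the probability, so the product cannot be evaluated.

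**The case against.** The strongest reply is that nothing is lost and that the definition is a legitimate choice. Requiring a reading favors specificity and is close to the stopping criterion. The event remains in the general by-arm tables. The safety board trigger is worded more broadly. Section 9.3 leaves further detail to a SAP finalized before unblinding, which may contain an AESI term list. Phase 1 also suggests that most OH will fall inside the monitored window, and in the dose-ranging oncology study in Section 2.2.2, dose-limiting dizziness from OH was 0% at 20 mg every 4 hours.

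Most of this stands, and it limits the point to a reporting matter of probably small size. It does not remove the gap: the one stated criterion excludes the event, and no text in the reviewed document brings it back into the AESI row.

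Two stronger inferences are tempting, and the documents support neither.

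- **Phase 1 dizziness as a missed fraction.** In the 15 and 30 mg single-dose groups, 1 to 2 of 6 participants had dizziness on standing. Section 2.2.1.1 says: "No vital sign measurements were obtained at the time of these events; however, the preferred term of OH was recorded". A reader might take this as the share of OH that Table 3 would miss. But these events were not described as severe, so they would probably fail Table 3 on symptoms whatever the pressure. The fall was unmeasured, not shown to be absent. They followed untitrated single doses in healthy volunteers. They also show an unmeasured event being recorded as OH.
- **Drug decay as proof that the fall is gone.** With a half-life of about 2 hours (Section 8.6), a reader might compute the drug left when the participant reaches the site. That describes concentration, not blood pressure, and the delay would be an assumption. The comparative PK study also reported: "All OH events occurred at 1 hour after dosing, with the exception of 1 OH event that occurred at hour 8".

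**Conclusion.** The point holds as a cheap improvement. Read as written, Table 3 leaves a home syncope or presyncope without a captured fall out of the by-arm OH AESI summary. If the row follows the recorded term instead, inclusion depends on each investigator's choice of diagnosis.

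The size of any undercount cannot be estimated from the documents and is probably small. That judgment assumes that the phase 1 repeat-dose pattern, seen in small healthy-volunteer groups, carries over to patients and that titration works as the protocol expects.

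A reader might also infer that severe postural events escape safety reporting, that the safety board would not see them, or that the dose comparison is biased by a known amount. The documents support none of these. The conclusion assumes that no AESI term list elsewhere already groups these events; the reviewed text contains none.

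**What to change.** In Table 3 and Section 9.3.6, before unblinding, define one postural-event AESI group: syncope, presyncope and other severe postural adverse events, with or without a blood-pressure reading. Summarize it by arm. Beneath it, show BP-confirmed OH, using the current Table 3 definition unchanged, as a subset row.

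The cost is wording in two places, one adverse event grouping and one extra table row, all from data already collected. No visit, reading or stopping rule changes. The downside is that some syncope not caused by OH will enter the broader row; the subset row keeps the specific count. Setting the terms before unblinding also avoids choosing them after the arm results are known.
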